4.6 Efficacy endpoints

For further details on efficacy endpoints, see Section 14 (Appendix II) of the protocol. For the evaluation of tumor-response related endpoints, response is assessed by investigator and BIRC according to RECIST 1.1.

Response and progression evaluation will be performed according to the Novartis RECIST 1.1 guidelines, included in Section 14 (Appendix II) of the CINC280A2201 protocol.

The text below gives more detailed instructions and rules needed for programming of the analyses described in [Sections 2.7](#) and [2.8.1](#).

4.6.1 Implementation of RECIST guidelines

Disease progression

PD should only be assigned if it is confirmed by an objective assessment method as per RECIST 1.1 (e.g. radiologic scan, histology for bronchoscopy, photos for skin lesions). If a new lesion is detected using an objective assessment method other than radiologic scan, it should be entered on the 'New lesion' RECIST eCRF with appropriate method (or method='Other').

In particular, discontinuation due to disease progression or death due to progressive disease, without supporting objective evidence (as defined above), will not be considered as PD in the determination of BOR, the derivation of any efficacy endpoint or efficacy analysis.

Change in imaging modality

Per RECIST 1.1, a change in methodology can be defined as either a change in contrast use (e.g. keeping the same technique, like CT, but switching from with to without contrast use or vice-

versa, regardless of the justification for the change) or a change in technique (e.g. from CT to MRI, or vice-versa), or a change in any other imaging modality. A change from conventional to spiral CT and vice versa while keeping same contrast use (e.g. switching from spiral CT with contrast to CT with contrast) is not considered a change in imaging modality. A change in methodology will result by default in a UNK (unknown) overall lesion response assessment. However, a response assessment other than the Novartis calculated UNK response may be accepted from the investigator or BIRC if a definitive response assessment can be justified based on the available information. Potential discrepancies between the modality used and overall lesion response reported by the investigator (e.g. change in modality but investigator assessment of response is different from UNK) will be queried during the data validation process.

Determination of missing adequate tumor assessments

For the computation of ORR, patients without any radiological assessment after the start date of study drug will be counted as failure.

Partial or complete responses reported prior to any additional anticancer therapy will be considered for ORR computation irrespective of the number of missed assessments before response. In this section, the ‘missing adequate assessment’ is defined as assessment not done or assessment with overall lesion response equal to UNK. For the sake of simplicity, the ‘missing adequate assessment’ will also be referred as ‘missing assessment’.

As detailed in Section 14 (Appendix II) of the CINC280A2201 protocol, the PFS censoring and event date options depend on the presence and the number of missing tumor assessments. *For example, an event occurring after two or more missing assessments is censored in the analysis of PFS at the last adequate tumor assessment before the event date.*

An exact rule to determine whether there is none, one or two missing assessments is therefore needed. This rule will be based on the distance between the last adequate tumor assessment date and the event date.

If the distance is larger than threshold D_1 or D_2 then the analysis will assume one or two missing assessments, respectively. The threshold D_1 will be defined as the protocol specified interval between the tumor assessments plus the protocol allowed window around the assessments. Similarly, the threshold D_2 is defined as two times the protocol specified interval between the tumor assessments plus the protocol allowed window around the assessments. In this study, the protocol defined schedule of tumor assessment is every 6 weeks and each assessment is expected to be performed at the scheduled time point plus or minus 1 week, i.e. the window is 2 weeks, then any distance larger than $D_1 = 6+2 = 8$ weeks means one missing assessment and any distance larger than $D_2 = (2*6) + 2 = 14$ weeks means two missing assessments.

The same definition of D_2 will be used to determine the PFS censoring reason.

Possible censoring reasons for PFS are:

- 1: Ongoing without event
- 2: Lost to follow-up
- 3: Withdraw consent
- 4: Adequate assessment no longer available

5: New cancer therapy added

6: Event after ≥ 2 missing tumor assessments

PFS censoring reason is then derived by the following sequence of rules.

- If patient is considered to have a PFS event then PFS censoring reason is set to missing.
- Else if patient has had no baseline assessment then PFS censoring reason = 4.
- Else if patient has a PFS event after two or more missing assessments [If (PFS Event date \leq Censoring date and (PFS Event date - Date of last adequate tumor assessment (LATA) \geq D2)] then PFS censoring reason =6:
- Else if patient has no PFS event, and patient is censored at a date after two or more missing assessments ((Censoring date - Date of LATA) \geq D2) then PFS censoring reason = 4
- Else if censoring date equals the start date of further anti-neoplastic therapy then PFS censoring reason = 5
- Else if censoring date equals date of discontinuation due to consent withdrawal then PFS censoring reason = 3
- Else if censoring date equals date of discontinuation due to loss to follow-up then PFS censoring reason = 2
- Else if the censoring date equal the analysis cut-off date and the time between LATA and the cut-off is greater than D2 days then PFS censoring reason = 4
- Else if the censoring date equal the analysis cut-off date and the time between LATA and the cut-off is less than or equal to D2 days then PFS censoring reason = 1

Where censoring date = minimum(analysis cut-off date, start date of further anti-neoplastic therapy, date of discontinuation due to consent withdrawal, date of discontinuation due to loss to follow-up).

Non-measurable disease at baseline

As specified in Section 14 (Appendix II) of the CINC280A2201 protocol, the RECIST 1.1 criteria imply that only patients with measurable disease at baseline should be included in the study. If a patient without measurable disease is enrolled, the intent-to-treat (ITT) principle requires including these patients in the analyses. Hence, analyses will be based on FAS including patients with either measurable or non-measurable disease. Therefore, a rule needs to be specified on how to handle these cases.

As specified in Table 3-1 of Section 14 (Appendix II) of the CINC280A2201 protocol, overall lesion response can be derived for patients without measurable disease at baseline as follows ([Table 4-3](#)).

Table 4-3**Overall lesion response at each assessment: patients with non-target disease only**

Non-target lesions	New Lesions	Overall lesion response
CR	No	CR
Non-CR/Non-PD ¹	No	Non-CR/non-PD
UNK	No	UNK
PD	Yes or No	PD
Any	Yes	PD

¹ In general, the **non-CR/non-PD response** for these patients is considered equivalent to an SD response in endpoint determination.

Missing baseline tumor assessment

As specified in Section 14 (Appendix II) of the protocol, since the timing of PD cannot be determined for patients with missing baseline tumor assessment, these patients are censored in the PFS analysis at the start date of treatment. This rule, however, only applies to the ‘PD component’ of the PFS or DOR assessment.

Patients without baseline tumor assessment who die within D₂ distance from start date of treatment will be counted as having an event in the primary analysis of PFS. All deaths will be counted in the OS analysis regardless of presence or absence of the baseline tumor assessment.

Construction of waterfall graphs

The waterfall graphs will be used to depict the anti-tumor activity. These plots will display the best percentage change from baseline in the sum of the measured diameter of all target lesions based on the on-treatment assessments occurring prior to the first PD for each patient with measureable disease at baseline. The proportions of patients with various degrees of tumor shrinkage or growth can then represent a useful efficacy metric.

However, caution needs to be paid to the assessments, where an occurrence of a new lesion or worsening in non-target lesions (resulting in PD as an overall lesion response at given assessment) contradicts the measurements obtained on target lesions. These assessments will not be displayed as bars in the graph. If such a “contradicting” assessment represents the only post-baseline assessment for a patient, then the patient will be represented by a special symbol (e.g. *) in the waterfall graph.

The assessments with unknown target response and also assessments with unknown overall response will be excluded. Patients without any valid assessments will be completely excluded from the graphs.

The total number of patients displayed in the graph needs to be shown and this number will be used as a denominator when calculating the percentages of patients with tumor shrinkage and tumor growth. Footnote will explain the reason for excluding some patients (due to absence of any valid assessment).

Patient who have discontinued will be represented by a special symbol in the waterfall graph.

All possible assessment scenarios are described in [Table 4-4](#).

Table 4-4 Inclusion/exclusion of assessments used in waterfall graph

Criteria for inclusion/exclusion			Possible source of contradictions	
Target response	Overall lesion response	Include in waterfall	Non-target response	New lesion?
CR/PR/SD	PD	Yes but as * only	PD	any
CR/PR/SD	PD	Yes but as * only	Any	Yes
UNK	UNK or PD	No	Any	any
CR/PR/SD	UNK	No	UNK	No
CR/PR/SD	CR/PR/SD	Yes as a bar	SD/IR	No
PD	PD	Yes as a bar	Any	any

The following algorithm will be used to construct the graph:

1. Select “valid” post-baseline assessments to be included, i.e. for each patient and each assessment repeat the following four steps:
 - 1.1. Check the target lesion response and overall lesion response at each assessment. If at least one of them is UNK then exclude the whole assessment. Otherwise, go to step 1.2.
 - 1.2. Check the overall lesion response. If PD, then go to step 1.3. Otherwise, go to step 1.4
 - 1.3. Check target response. If PD, then go to step 1.4. Otherwise flag the assessment ★.
 - 1.4. Calculate the % change from baseline in target lesions.
2. For each patient, go through all valid assessments identified in step 1 and find the assessment with best % change from baseline in target lesions. The “best” means best for the patient, i.e. the largest shrinkage or if a patient only has assessments with tumor growth take the assessment where the growth is minimal. (*Example 1*: Patient 1 has the following % changes from baseline at assessments 1, 2, 3, 4 and 5, respectively: -10%; -25%; -13%; -4% and +6%. His/her best % change is then -25%. *Example 2*: Patient 2 has the following % changes from baseline at assessments 1, 2 and 3, respectively: +5%; +18% and +35%. His/her best % change is then +5%).
3. Construct the waterfall graph displaying the best % change from baseline for each patient. Patients having only ★ flagged assessment(s) will be displayed separately.

Both investigator assessment and BIRC will be used in the construction of waterfall plot.

The recommended way of the display from left to right is:

1. Bars under the horizontal axis representing tumor shrinkage
2. Bars above the horizontal axis representing tumor growth
3. “Zero” bars with ★ symbol representing patients with contradiction

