## 7 Visit schedule and assessments

### 7.1 Study flow and visit schedule

Table 7-1 lists all the assessments and indicates with an “X”, the visits when they are performed. All data obtained from these assessments must be supported in the patient’s source documentation. The table indicates which assessments produce data to be entered into the database (D) or remain in the source documents only (S) (“Category” column). The eCRF will not be used as a source document.

Written informed consent must be obtained before any study specific assessments are performed, including those at molecular screening and screening. Main screening evaluations and baseline radiological tumor assessments should be performed within 28 days of treatment start.

Each treatment cycle is 21 days (the 21 days cycle length is fixed regardless of whether the dose of INC280 is withheld).

All visits are to be scheduled according to the appropriate number of calendar days from Cycle 1 Day 1 of study drug administration. Every effort must be made to follow the schedule of assessments within the windows outlined in the protocol.

After screening:

- All assessments have a  $\pm 3$  day window unless otherwise indicated
- Radiological tumor assessments may be performed within a  $\pm 4$  day window, unless otherwise indicated
- If a given visit is out of window, the next visit should be performed with reference to the day of first dose in order to get the patient back on schedule
- If an off-schedule imaging assessment is performed, subsequent imaging assessments should be performed in accordance with the original imaging schedule
- Laboratory assessments and height/weight performed as part of the screening evaluations and within 7 days of the first dose of study drug, will not be required to be repeated on Cycle 1, Day 1
- All assessments on Cycle 1, Day 1 must be done prior to the first dose unless otherwise specified. It is recommended that the investigator checks the pre-dose laboratory results prior to starting treatment
- Patients who discontinue INC280 treatment must have EOT visit performed  $\leq 7$  days after stopping study drug
- Permitted contact windows for survival follow-up:  $+\text{-} 7$  days

Additional assessments may be performed as clinically indicated.

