#### **7.2.1.2 Subsequent imaging for response assessment**

Imaging assessments as described in [Table 7-2](#) should be performed at the timepoints specified using the same imaging modality used at baseline, irrespective of study treatment interruption or actual dosing (see [Table 7-1](#)). Imaging assessments for response evaluation will be performed every 6 weeks starting from Day 1 of cycle 1 (+/- 4 days window).

Additional imaging assessments may be performed at any time during the study at the investigator's discretion to support the efficacy evaluations for a patient, if necessary. Clinical suspicion of disease progression at any time requires a physical examination and imaging assessments to be performed promptly rather than waiting for the next scheduled imaging assessment.

Each lesion that is measured at baseline must be measured by the same method (either same imaging method or by photography, including a metric ruler) and when possible, the same local radiologist/physician throughout the study so that the comparison is consistent. If an off-schedule imaging assessment is performed because progression is suspected, subsequent imaging assessments should be performed in accordance with the original imaging schedule.

Combined PET/CT may be used only if the CT is of similar diagnostic quality as a CT performed without PET, including the utilization of oral and IV contrast media. At the discretion of the Investigators, FDG-PET scans may be performed to document PD per RECIST 1.1 ([Appendix 1](#)).

All study imaging (including any off-schedule imaging studies) performed to evaluate progression or response should be submitted to the designated imaging vendor for quality control and review by the BIRC, promptly after acquisition.

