### **End dates**

The end dates which are used to calculate ‘time to event’ variables are defined as follows:

- Date of death (during treatment as recorded on the treatment completion page or during follow-up as recorded on the study evaluation completion page or the survival follow-up page).
- Date of progression is the first assessment date at which the overall lesion response was recorded as progressive disease.
- Date of last adequate tumor assessment is the date the last tumor assessment with overall lesion response of CR, PR or SD which was made before an event or a censoring reason occurred. In this case the last tumor evaluation date at that assessment is used. If no post-baseline assessments are available (before an event or a censoring reason occurred) the date of randomization/start of treatment is used.
- Date of next scheduled assessment is the date of the last adequate tumor assessment plus the protocol specified time interval for assessments. This date may be used if back-dating is considered when the event occurred beyond the acceptable time window for the next tumor assessment as per protocol (see [Section 14.1.26](#)).

**Example** (if protocol defined schedule of assessments is 3 months): tumor assessments at baseline - 3 months - 6 months - missing - missing - PD. Date of next scheduled assessment would then correspond to 9 months.

- Date of discontinuation is the date of the end of treatment visit.
- Date of last contact is defined as the last date the patient was known to be alive. This corresponds to the latest date for either the visit date, lab sample date or tumor assessment date. If available, the last known date patient alive from the survival follow-up page is used. If no survival follow-up is available, the date of discontinuation is used as last contact date.
- Date of secondary anti-cancer therapy is defined as the start date of any additional (secondary) antineoplastic therapy or surgery.

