- No valid post-baseline assessment
- All post-baseline assessments have overall response UNK
- New anti-neoplastic therapy started before first post-baseline assessment
- Stable disease (SD) too early (≤ 6 weeks after start date of study drug*)
- PD too late (> 12 weeks after start date of study drug*)

Special (and rare) cases where BOR is 'unknown' due to both early SD and late PD will be classified as 'SD too early'.

*Thresholds for SD too early and PD too late are defined as the protocol-specified time interval + protocol-allowed time windows (± 4 days) around the tumor assessments.

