2.8 Analysis of secondary variables

2.8.1 Efficacy

All secondary endpoint analyses will be performed based on the FAS, unless otherwise specified. Efficacy will also be presented combining the MET mutant cohorts per line of treatment as defined in [Section 2.2](#).

No adjustment for multiple testing will be made.

Key secondary efficacy endpoints

The key secondary objective is to evaluate duration of response (DOR) as assessed by BIRC, by cohort.

Among patients with a confirmed response (PR or CR), DOR is defined as the time from first documented response (PR or CR) to the date of first documented PD or death due to any cause. If a patient has not had an event, DOR is censored at the date of last adequate tumor assessment.

The censoring and event date options to be considered for the main analysis are presented in [Table 2-1](#).

Table 2-1 Outcome and event dates for DOR and PFS analyses

Situation	Date	Outcome
A No baseline assessment	Date of first dose of study drug ^a	Censored
B Progression at or before next scheduled Assessment	Date of progression	Progressed
C1 Progression or death after exactly one missing assessment	Date of progression (or death)	Progressed
C2 Progression or death after two or more missing assessments	Date of last adequate assessment	Censored
D No progression	Date of last adequate assessment	Censored
E Treatment discontinuation due to 'Disease progression' without documented progression, i.e. clinical progression based on investigator claim	N/A	Information ignored. Outcome derived based on radiology data only.
F New anticancer therapy given	Ignore the new anticancer therapy and follow situations above	As per above situations
G Deaths due to reason other than deterioration of 'Study indication'	Date of death	Progressed

^a The rare exception to this is if the patient dies no later than the time of the second scheduled assessment as defined in the protocol in which case this is a PFS event at the date of death

DOR will be described in tabular and graphical format using Kaplan-Meier methods. The Kaplan-Meier estimate of the distribution function will be constructed. Kaplan-Meier curves

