Table 2-10 Number of Responders for Various Number of Evaluable Patients at Interim Analyses by Required Probability of Success for Cohort 1a, Cohort 1b, Cohort 2 and Cohort 4

Number of Evaluable patients at IA	Responders at IA	Probability of Success
26	6	0.0368
26	7	0.1050
27	7	0.0765
27	8	0.1829
28	7	0.0543
28	8	0.1398

Number of Evaluable patients at IA	Responders at IA	Probability of Success
29	7	0.0377
29	8	0.1044
30	8	0.0760
30	9	0.1792
31	8	0.0540
31	9	0.1369
32	8	0.0373
32	9	0.1020
33	9	0.0740
33	10	0.1739
34	9	0.0523
34	10	0.1323
35	10	0.0980
35	11	0.2152

Cohort 3

With 20 evaluable patients for interim analysis in Cohort 3 if ≤ 5 responses (POS=0.0999) are observed then the cohort will be stopped for futility. All evaluable patients at the time of the data cut-off for the interim analysis will be used to obtain the futility boundary using the POS criteria. Further details of POS are provided in [Table 2-11](#). If at the time that the 20th patient is enrolled a minimum of 6 responders have not yet been observed, accrual in the cohort may be temporarily suspended until either the minimum number of 6 responders are observed or results of the interim analysis allow the cohort to continue.

Table 2-11 Probability of Success at the Final Analysis Based on Various Number of Responders Observed at IA for Cohort 3 (MET GCN less than 4)

Responder at IA out of 20 evaluable patients at IA	Probability of Success
1	0.0001
2	0.0009
3	0.0066
4	0.0309
5	0.0999
6	0.2379
7	0.4382
8	0.6533

3 Changes to protocol specified analyses

Not applicable.

4 Additional details on implementation of statistical methodology

The sections below contain additional details on statistical methodology that will be included in Appendix 16.1.9 (Documentation of Statistical Methods) of the CSR as well as rules details on programming rules that will be followed to implement the analyses described in [Section 2](#).

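### SAP 4.6.1 builds its missing-scan thresholds on a ±1 week window although the protocol allows ±4 days: the two-scan threshold D2 should be 92 days, not 98, with a small effect on PFS and DOR

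*SAP*

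**What the plan says.** SAP 4.6.1, under the determination of missing adequate tumor assessments, measures the distance from the last adequate assessment to the event. D1 is one protocol scan interval, and D2 is two, in each case "plus the protocol allowed window around the assessments". For this study the SAP then states that "each assessment is expected to be performed at the scheduled time point plus or minus 1 week, i.e. the window is 2 weeks", and obtains D1 = 8 weeks and D2 = 14 weeks.

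Three other places give a different window:
- Protocol 7.1: "Radiological tumor assessments may be performed within a" window of ±4 days. The ±7 days in the same list applies to survival contacts only.
- Protocol 7.2.1.2: imaging is "every 6 weeks starting from Day 1 of cycle 1 (+/- 4 days window").
- SAP 2.7.1, for the best-overall-response thresholds: "protocol-allowed time windows (± 4 days) around the tumor assessments".

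SAP Table 2-1 applies to both DOR and PFS. Rows B and C1 (no missing assessment, or exactly one) count the event on its actual date. Row C2 (two or more missing) censors at the last adequate assessment. SAP 4.6.1 also uses D2 to assign PFS censoring reasons.

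For a patient with no baseline assessment, row A censors at first dose. Footnote a adds: "The rare exception to this is if the patient dies no later than the time of the second scheduled assessment", in which case the death is a PFS event. Protocol Table 14-5, footnote 3, says the same. SAP 4.6.1, under missing baseline tumor assessment, instead counts deaths within D2 of treatment start.

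**The concern.** The SAP says that its thresholds are built from the protocol's window and then enters a window that the protocol does not contain. The programmed rule is therefore not the rule that the text defines. D2 is a decision threshold: it turns an event into a censored record for DOR by BIRC, the key secondary endpoint, and for PFS. A value that is too long keeps as events some deaths and progressions that the stated rule would censor.

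A smaller wording problem sits beside it. The early-death cut-off for patients with no baseline assessment is given in two ways, and both cannot be programmed.

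**Working it through.** **Inputs.** Scan interval 6 weeks = 42 days (protocol 7.2.1.2). Window ±7 days in SAP 4.6.1, and ±4 days in protocol 7.1, protocol 7.2.1.2 and SAP 2.7.1. The SAP adds the full width of the window, which is 14 or 8 days.

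**Reproducing the SAP.** D1 = 42 + 14 = 56 days (8 weeks) and D2 = 2 × 42 + 14 = 98 days (14 weeks). Both match. A half-width convention would give D2 = 84 + 7 = 91, and 2 × (42 + 14) would give 112. Neither matches, so full width is the SAP's own convention.

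**With the protocol window.** D1 = 42 + 8 = 50 days and D2 = 84 + 8 = 92 days.

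**Which records change.** D1 only separates rows B and C1, which have the same outcome. D2 changes row C2 status for distances of 93 to 98 days, which is six days. PFS censoring reasons based on D2 can change over the same span.

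**Progressions on the Day 1 schedule.** If both scans are in window, the gap is 84 ± 8 = 76 to 92 days after one missed scan and 126 ± 8 = 118 to 134 days after two. Both values of D2 classify these alike, provided that a gap of exactly 92 days counts as one missed scan.

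**Progressions at post-treatment scans.** Protocol 7.1.5.2 times these scans from EOT, whereas protocol 4.1.4 keeps the current schedule. Table 7-1 waives the EOT scan if one was done within 28 days. If the last scan was g days before EOT, progression after one missed follow-up scan falls at g + 84 ± 4 days. For g = 5 that is 85 to 93 days, and for g = 18 it is 98 to 106 days. Values of g from 5 to 18 can therefore land on days 93 to 98.

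**Deaths.** Assume a constant hazard h after the last adequate scan and no further scan. The share dying on days 93 to 98 is exp(−92h) − exp(−98h):

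| Median (months) | 1 | 2 | 3 | 6 | 12 | 24 |
|---|---|---|---|---|---|---|
| Share (%) | 1.57 | 2.32 | 2.21 | 1.59 | 0.95 | 0.52 |

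The maximum over all h is 2.32%, at a median of 2.16 months. With the combined cohorts in SAP 2.2, that is 0.0232 × 100 = 2.3 pretreated and 0.0232 × 60 = 1.4 treatment-naïve patients, even if every patient stopped scanning. If 10% to 30% did (an assumption), the maxima are 0.23 to 0.70 and 0.14 to 0.42 patients.

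**Early-death cut-off.** The second scheduled assessment is Cycle 5 Day 1, study day 85 (SAP Table 4-6), which is 84 days after first dose. Against D2 the wordings differ for deaths on days 85 to 98 as written, or 85 to 92 with D2 corrected. If the footnote is read with its +4 days (88 days), the spans are 89 to 98 and 89 to 92.

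**The case against.** The mismatch itself is hard to dispute. The case against giving it weight has several parts.

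- *Almost nothing changes.* This stands as to size. The death counts above are below one patient under the 10% to 30% assumption. They use whole cohorts, whereas DOR includes only confirmed responders, so the DOR count is smaller still.
- *It is not a departure from the protocol.* A reader might infer that SAP Section 3, "Changes to protocol specified analyses", marked as not applicable, hides a changed protocol threshold. The documents do not support that. The protocol defines no D1 or D2, and Table 14-5 speaks only of two or more missing assessments. The fault is internal to the SAP.
- *92 days is not always the better value.* This stands in part. For scans timed from EOT, 92 days can censor a progression that followed only one missed scan, where 98 days would keep it. It would be too strong to say that on-schedule progressions are never affected.
- *92 days sits on an awkward boundary.* This stands. SAP 4.6.1 defines missing assessments by distances strictly above D2 but assigns two censoring reasons with ≥ D2, and later uses strictly greater again. A gap of exactly 92 days can arise from two in-window scans, so the inequality has to be settled together with the constant.
- *A change this late is data-aware.* SAP 2.1 lists four data cut-offs already analyzed. The documents do not show whether those analyses used 98 days. This supports a declared alternative, not silence.

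**Conclusion.** The SAP is wrong as written, with a small effect. Under its own full-width formula and the protocol's ±4 days, D1 is 50 days and D2 is 92. Only events 93 to 98 days after the last adequate assessment change status: mainly deaths, off-schedule progressions, and progressions at post-treatment scans timed from EOT. ORR is unaffected, and PFS and DOR are descriptive. The 2.3% ceiling rests on a constant hazard and covers deaths only. The documents give no counts for the other two groups.

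On early deaths, the two wordings do conflict, but the point is minor. It concerns only patients with no baseline assessment, which SAP 2.2 lists as a major deviation, and their number is not given. Two stronger readings do not hold:
- A cut-off of 92 days does not simply implement the footnote. Read literally, the footnote means 84 days.
- The sentence in SAP 2.8.1 that censors patients with no BIRC data at first dose does not merely lack a death exception. Those patients overlap only in part with patients who have no baseline assessment, so an exception there would be a new event rule, not a correction.

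**What to change.** In SAP 4.6.1, replace the ±1 week statement with ±4 days (full width 8 days), and set D1 = 50 days and D2 = 92 days. Use one inequality, distance > D2, in the definition and in every censoring-reason rule, so that a gap of exactly 92 days counts as one missed scan. The follow-up scan timing in protocol 4.1.4 and 7.1.5.2 should be reconciled, because it bears on how the threshold works after treatment.

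If 98 days was used at the earlier cut-offs and is kept for comparability, state openly that ±1 week is an analysis tolerance wider than the protocol window, and show PFS and DOR with D2 = 92 as a sensitivity analysis.

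Use one early-death cut-off in Table 2-1 footnote a and in SAP 4.6.1. D2 has a consistency argument. For patients with a baseline scan and no later one, protocol 14.1.25 already measures from treatment start: "If no post-baseline assessments are available (before an event or a censoring reason occurred) the date of randomization/start of treatment is used". If D2 is chosen, record it as a departure from the footnote's literal wording. Leave the no-BIRC-data sentence in SAP 2.8.1 as it is.

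The cost is a few sentences, two programming constants and one aligned inequality. A few PFS or DOR records may differ in status from earlier reports, and the CSR should say so.
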